- Other medications when prescribed for wAIHA (e.g. rituximab or other anti-CD20 monoclonal antibody, cyclosporine, ibrutinib or other BTK inhibitor, chemotherapy agents such as cyclophosphamide, vincristine, investigational agents for AIHA, etc.), are not allowed during study treatment (from Day 1 until the last dose of study drug).
- Subjects requiring any AIHA therapies other than those allowed or an escalation of the allowed medications other than steroids should be withdrawn from the study. The Medical Monitor should be consulted in these instances.

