## 5.9 Allowed AIHA Therapies

Subjects may continue concurrent steroid therapy and other wAIHA therapy (maximum of 2 therapies) as listed in [Section 7.14.1](#).

Doses and regimens of concurrent wAIHA therapies allowed at entry may not be changed during the 24-week treatment period except for temporary steroid dose increases instituted as rescue therapy or a steroid taper as allowed by the protocol (see [Section 7.9](#) for Rescue Protocol and [Section 7.10](#) for Steroid Taper Protocol).

If an allowed medication is discontinued during screening, the interval between last dose of medication and randomization is per the time frames listed in [Section 7.14.1](#).

Other medications prescribed for wAIHA, e.g. rituximab or other anti-CD20 monoclonal antibody, cyclosporine, brutinib or other BTK inhibitor, chemotherapy agents such as cyclophosphamide, vincristine, investigational agents for AIHA, etc., are not allowed during study treatment (from Day 1 until the last dose of study drug).

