## 6.2 Exclusion Criteria

1. Subject with other types of AIHA (e.g., cold antibody AIHA, cold agglutinin syndrome, mixed type AIHA, or paroxysmal cold hemoglobinuria).
2. Subject has AIHA secondary to autoimmune disease, including systemic lupus erythematosus (SLE), or lymphoid malignancy if the underlying disease is not stable or is not well-controlled on current therapy, per investigator medical judgment.
3. Subject has a history of or active, clinically significant, cardiovascular, respiratory, gastrointestinal, renal, hepatic, neurological, psychiatric, musculoskeletal, genitourinary, dermatological, or other disorder that, in the investigator's opinion, could affect the conduct of the study or the absorption, metabolism or excretion of the study drug.
4. Subject has uncontrolled or poorly controlled hypertension, defined as systolic blood pressure  $\geq 135$  mmHg or diastolic blood pressure  $\geq 85$  mmHg, whether or not the subject is receiving anti-hypertensive treatment.
5. Subject has one or more of the following laboratory abnormalities at screening: neutrophil count of  $< 1,000/\mu\text{L}$  or platelet count of  $< 30,000/\mu\text{L}$ , unless due to Evans syndrome; transaminase levels (i.e., alanine aminotransferase [ALT] or aspartate aminotransferase [AST])  $> 1.5 \times \text{ULN}$ .
6. Has documented HIV infection or active hepatitis B or hepatitis C infection.
7. Subject is currently enrolled in an investigational drug or device study or has used an investigational drug or device within 30 days or 5 half-lives (whichever is longer) of Day 1.
8. In the judgment of the investigator, the subject may not be able to fully comply with study requirements.
9. Subject has been treated with fostamatinib previously for any indication.
10. Subject has a known allergy and/or sensitivity to the test article or its components.
11. Subject has had a splenectomy within the past 4 weeks.

Exemptions or exceptions to the inclusion or exclusion criteria are not allowed.

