## 6.3 Disallowed AIHA Therapies

**Disallowed AIHA Therapies:** Any of the disallowed therapies below in [Table 3](#) may not be taken within the indicated interval prior to Day 1.

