## 7.1 Screening

### 7.1.1 Screening Visit (Day -28 to -1)

Subjects must be willing to sign and date an Institutional Review Board (IRB)-approved informed consent form (ICF) prior to participating in any study-specific screening procedure activities.

Screening evaluations will be used to determine the eligibility of each subject prior to initiation of treatment.

Screening assessments may be repeated up to two additional times during the 28-day screening window. This restriction does not apply to instances where the result was not obtained such as a hemolyzed laboratory sample.

Subjects who fail to meet eligibility criteria or have screening assessments performed outside of 28 days of randomization should be rescreened.

Subjects who fail to meet eligibility criteria may be re-screened up to two times if there is a reasonable expectation that the subject will be eligible after the repeat screen(s) (for example, following successful treatment of hypertension).

Sites will be required to complete and send an eligibility verification form to the Medical Monitor for review and approval prior to randomizing a subject.

The following assessments will be completed as part of the screening visit (up to 28 days prior to Baseline/Day 1):

- Inclusion/Exclusion Criteria
- Demographics: sex, race/ethnicity and age
- Medical and wAIHA treatment history
- Physical examination and KPS
- Height and weight
- Prior and Concomitant Medications (30 days prior to baseline for prior non-AIHA meds; all prior AIHA therapies prior to baseline)
- Vital Signs, including blood pressure, should be taken with the subject seated and after the subject rests for 5 minutes. If the blood pressure is outside the parameters for inclusion ( $\geq 135$  mmHg systolic, or diastolic blood pressure  $\geq 85$  mmHg), the subject should remain seated and the measurement should be taken 2 more times at least 3 minutes apart. The average of these 3 measurements will be used to determine eligibility.
- 12-Lead ECG

- DAT (results must be positive for anti-IgG or IgA; historical results are acceptable within 12 months of screening from a local laboratory; otherwise testing will be done centrally).
- Complete Blood Count (CBC) with differential
- Serum Chemistry (with LFTs)
- Haptoglobin
- Urinalysis
- Serum Pregnancy Test (for females of childbearing potential)

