#### 7.14.1 Allowed AIHA Therapies

Subjects may continue concurrent steroid therapy and other wAIHA therapy (maximum of 2 therapies) as listed below throughout their participation in the study (note: throughout this document the term 'steroid' indicates corticosteroid drugs as well as glucocorticoids). If an allowed medication is discontinued during screening, the interval between last dose of medication and randomization must meet the time frames listed in the table below:

Medication	Number of weeks required to be at stable dose prior to randomization	Minimum required interval between discontinuation and randomization
Azathioprine	4 weeks	4 weeks
Steroids, including dexamethasone	2 weeks	2 weeks
Erythropoiesis-stimulating agents	4 weeks	4 weeks
Mycophenolate Mofetil	4 weeks	4 weeks
Dapsone	4 weeks	4 weeks
Danazol	4 weeks	4 weeks

Doses and regimens of concurrent wAIHA therapies allowed at entry may not be changed during the 24-week treatment period except for temporary steroid dose increases instituted as rescue therapy or a steroid taper as allowed by the protocol (see [Section 7.9](#) for Rescue Protocol and [Section 7.10](#) for Steroid Taper Protocol).

If Promacta is being given as a concurrent medication, the dose must be stable for 4 weeks prior to randomization.

Splenectomy and other medications when prescribed for wAIHA (e.g., rituximab or other anti-CD20 monoclonal antibody, cyclosporine, ibrutinib or other BTK inhibitor, chemotherapy agents such as cyclophosphamide, vincristine, investigational agents for AIHA, etc.) are not allowed during study treatment (from Day 1 until the last dose of study drug). Subjects requiring any AIHA therapies other than those allowed, or an escalation of the allowed medications other than steroids should be withdrawn from the study. The Medical Monitor should be consulted in these instances.

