### **10.3.6 Analysis of Primary Efficacy Endpoint**

The primary efficacy endpoint is achievement of durable hemoglobin response (Yes/No) defined as achieving a hemoglobin level  $\geq 10$  g/dL with an increase from Baseline in hemoglobin level of  $\geq 2$  g/dL on 3 consecutive available visits during the 24-week treatment period, in which hemoglobin measurements eligible for this definition occurred outside a Rescue Treatment Visit Exclusion Period.

Available visits are defined as any scheduled visit where a plasma sample was collected, and hemoglobin level analyzed using either central or local laboratory.

For permitted rescue medications, a Rescue Treatment Visit Exclusion Period begins with the initiation of the rescue medication. The end of a Rescue Treatment Visit Exclusion Period is 4 weeks (28 days) following the return of steroid use to Baseline level or the last administration of rescue medication, whichever event occurs the latest. Any hemoglobin measurements made during this exclusion period are not eligible for any endpoint definition.

For non-permitted rescue medications, a Rescue Treatment Visit Exclusion Period begins with the initiation of the rescue medication and ends at Week 24/Week 26 or date of early termination from study.

If durable hemoglobin response cannot be determined because the subject discontinued from the study prior to attaining a durable response, then the subject will be assumed as not having achieved a durable response.

Analysis will be performed after all randomized subjects have completed the 24 weeks of treatment or discontinued from the study. All subjects randomized will be included in the analysis (ITT population). The following hypothesis will be evaluated:

$$H_0: \Theta_{\text{Fostamatinib,Placebo}} = 1$$

$$H_a: \Theta_{\text{Fostamatinib,Placebo}} \neq 1,$$

where  $\Theta_{\text{Fostamatinib,Placebo}}$  is the odds ratio of durable hemoglobin response due to treatment.

Analysis will be performed using Cochran-Mantel-Haenszel (CMH) test stratified by concomitant steroid use at Baseline ( $\geq 20$  vs.  $< 20$  mg daily), and screening hemoglobin level ( $< 9$  vs.  $\geq 9$  g/dL). The odds ratio will be presented along with the 95% CI. The study will be considered to meet its primary efficacy objective if the lower bound of the 95% CI of the odds ratio of durable hemoglobin response between the Fostamatinib and Placebo-treated subjects is greater than 1.

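### Hemoglobin rises after AIHA-active treatment given for another disease can count as a durable response, because the on-treatment ban is worded by indication and hemoglobin is discarded only after rescue medication

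*Combined protocol and SAP*

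**What the plan says.** **Ban during treatment.** Three places state it, each limited by indication:
- Section 7.14.1: "Splenectomy and other medications when prescribed for wAIHA (e.g., rituximab or other anti-CD20 monoclonal antibody".
- Section 5.9: "Other medications prescribed for wAIHA, e.g. rituximab or other anti-CD20 monoclonal antibody".
- Synopsis, Allowed AIHA Therapies: "Other medications when prescribed for wAIHA (e.g. rituximab or other anti-CD20 monoclonal antibody, cyclosporine, ibrutinib or other BTK inhibitor".

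**Washout before treatment.** Section 6.3 says of the agents in Table 3 that they "may not be taken within the indicated interval prior to Day 1". The sentence and the table give agents and intervals and do not mention the reason for prescribing.

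**Which hemoglobin values are discarded.** Section 10.3.6 has two triggers: "For permitted rescue medications, a Rescue Treatment Visit Exclusion Period begins with the initiation of the rescue medication" and "For non-permitted rescue medications, a Rescue Treatment Visit Exclusion Period begins with the initiation of the rescue medication and ends at Week 24/Week 26". Values inside the period are ineligible for every endpoint. Section 7.9 allows rescue after a hemoglobin fall of more than 1.5 g/dL from baseline or new or worsening anemia symptoms, when treatment is urgent. Non-permitted rescue medications are not defined.

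**Who can enter.** Section 6.2 excludes a subject only under this condition: "Subject has AIHA secondary to autoimmune disease, including systemic lupus erythematosus (SLE), or lymphoid malignancy if the underlying disease is not stable" or not well controlled. The neutrophil and platelet limits are waived for Evans syndrome.

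**What is recorded.** Section 7.1.1 collects prior medication as follows: "30 days prior to baseline for prior non-AIHA meds; all prior AIHA therapies prior to baseline".

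**The concern.** The rule narrows at the moment hemoglobin starts to count. Before Day 1 an anti-CD20 agent, BTK inhibitor, cyclosporine or chemotherapy matters as an agent. From Day 1 it matters only if prescribed for wAIHA. The endpoint does not close the gap, because its exclusion period opens only for rescue.

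The population makes this a practical matter. Subjects with SLE, lymphoid malignancy or Evans syndrome have a second disease that may be treated with the same agents. The clearest case is an anti-CD20 agent or BTK inhibitor given for lymphoid malignancy. A steroid course for lupus and IVIg for platelets are further cases, subject to how rescue is read.

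In the placebo arm such responses dilute the effect; in the fostamatinib arm they are credited to the drug. They also enter secondary endpoints 1 to 3 (response on at least one visit, a rise of at least 2 g/dL, and change to End of Treatment), which use the same hemoglobin values.

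**Working it through.** **1. Does any other rule catch these values?**

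| Rule | Keyed to | Catches an anti-CD20 agent or BTK inhibitor given for lymphoid malignancy? |
|---|---|---|
| On-treatment ban (synopsis, 5.9, 7.14.1) | prescribed for wAIHA | No |
| Restricted medications unrelated to AIHA (7.14.2) | drug-drug interactions | No |
| Withdrawal (7.6, 7.14.1) | AIHA therapies not allowed, or escalation of allowed agents other than steroids | Only if AIHA therapies is read by agent |
| Exclusion period (10.3.6) | rescue medication | Not as rescue is described in 7.9 |
| Major-deviation example (10.3.2) | non-permitted rescue medications | Term undefined |
| Sensitivity analyses (10.3.6) | prognostic imbalance, imputation, 6-week washout | No |

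No rule clearly removes the values.

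**2. Look-back against washout.** Non-AIHA prior medication is recorded for 30 days. Table 3 requires 6 weeks (42 days) for chemotherapy and 8 weeks (56 days) for anti-CD20 agents. For use under another indication, the last 12 and 26 days of those intervals fall outside the record.

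**3. The plan's own power figure.** Inputs from Section 10.1: 27% (7/26) vs 5%, 45 per arm, two-sided 0.05, Fisher's exact test, at least 84% power. Exact enumeration of all 46 × 46 outcomes gives 78.0% for Fisher. Normal approximations give 82.4% (pooled) and 84.7% (unpooled). The stated figure therefore fits an approximation rather than the test it names. That is a separate matter, and nothing below depends on it.

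**4. How many spurious responders matter?** Expected responders are 45 × 0.27 = 12.15 and 45 × 0.05 = 2.25, so about 12 vs 2. Section 10.3.6 judges success by the CMH analysis, with the lower 95% bound of the odds ratio above 1. The documents give no stratum counts, so the check is unstratified. With a = fostamatinib responders, m = all responders and N = 90:

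χ² = (a − m/2)² / V, where V = 45 × 45 × m(N − m) / [N²(N − 1)].

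- 12 vs 4: m = 16, V = 3.326, χ² = (12 − 8)²/3.326 = 4.81, p = 0.028. OR = (12 × 41)/(4 × 33) = 3.73.
- 12 vs 5: m = 17, V = 3.486, χ² = (12 − 8.5)²/3.486 = 3.51, p = 0.061. OR = (12 × 40)/(5 × 33) = 2.91.

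The 95% CI is exp[ln OR ± 1.96 × √(sum of the four reciprocal cell counts)].

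| Placebo responders (of 45), against 12/45 | CMH p | OR (95% CI) | Fisher p |
|---|---|---|---|
| 2 | 0.004 | 7.82 (1.64 to 37.4) | 0.007 |
| 3 | 0.011 | 5.09 (1.33 to 19.5) | 0.021 |
| 4 | 0.028 | 3.73 (1.10 to 12.6) | 0.051 |
| 5 | 0.061 | 2.91 (0.93 to 9.10) | 0.104 |

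From a base of 2, the CMH criterion fails at 5, which is three extra placebo responders.

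**5. Expected effect over assumed counts** (unstratified CMH, exact enumeration). The counts and percentages added are assumptions.

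| Assumption | None added | Added spurious response | Result |
|---|---|---|---|
| Placebo only, base 27% vs 5% | power 86.2% | 1 / 2 / 3 expected responders | power 74.2 / 60.3 / 46.4% |
| Both arms, same chance among non-responders | power 86.2% | 2 / 5 / 10% | power 80.7 / 72.1 / 59.5% |
| Fostamatinib only, true rate 5% in both arms | false-win chance 2.1% | 1 / 2 / 3 expected responders | false-win chance 5.5 / 11.0 / 19.0% |

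**The case against.** **Rescue may be meant by agent.** Section 7.9 counts increases in steroid dose among rescue medications, and Section 10.3.6 ends the period when steroid use returns to Baseline level. Read that way, steroids and IVIg given for another disease are already caught. The reading is open but the text does not settle it, and it leaves anti-CD20 agents and BTK inhibitors unresolved.

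**The before-and-after contrast depends on a label.** Table 3 is itself headed as disallowed AIHA therapies. If AIHA therapy means the agent throughout, the withdrawal rule and the full look-back for AIHA therapies would reach these drugs. This is a fair point, and it is why the passages need reconciling. The ban's own wording still runs by indication in all three places.

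**Stronger readings that the documents do not support:**
- A reader might infer that every such treatment slips through. Raising an existing MMF dose is caught by the escalation clause in Sections 7.6 and 7.14.1, which is not limited by indication. A transfused bleed would usually meet the rescue trigger, which ignores cause. Splenectomy in Section 7.14.1 can be read as barred outright, although a literal trigger on medication does not open for surgery.
- A reader might infer that two spurious placebo responders lose the trial. That holds only for Fisher's test, which the plan uses only for sample size.
- A reader might apply the background shares in Section 3.1 (20% autoimmune, 20% lymphoproliferative) and count 0.40 × 90 = 36 subjects at risk. Those shares describe the disease, not this trial's enrollment or drug use.

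**Likelihood is limited.** The underlying disease must be stable, the Medical Monitor approves each eligibility form, and a durable response needs three consecutive qualifying visits. These lower the chance without removing it.

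**The SAP may add rules.** The protocol defers detail to it. Section 10.3.6 nevertheless defines the endpoint and the exclusion period, and is silent on this.

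**Conclusion.** The concern holds in this form. The ban runs by indication, hemoglobin is discarded only after rescue, and eligible subjects may have a second disease treated with the same agents. The plan as written therefore allows a treatment-confounded rise to count as a durable response in either arm. The firmest case is an anti-CD20 agent or BTK inhibitor given for lymphoid malignancy. The steroid and IVIg cases depend on how rescue is read.

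The size is conditional. With about 12 vs 2 responders expected, three spurious placebo responders would turn a win into a loss under the CMH criterion. One to three expected in the fostamatinib arm, with no true effect, would raise the false-win chance from 2.1% to between 5.5% and 19.0%. These figures rest on assumed counts, the planning rates and an unstratified calculation; stratification could shift them slightly. They show how sensitive the result is, not how often the event would occur. The change should be made before unblinding.

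**What to change.** 1. **Section 10.3.6 and the SAP derivation.** Define the Rescue Treatment Visit Exclusion Period by treatment received, not by label or indication.
   - Any RBC transfusion, IVIg or systemic steroid increase above Baseline opens the existing period that ends 28 days after the later of last administration and return to Baseline steroid level.
   - Any Table 3 agent not on the permitted rescue list, splenectomy, or the start or increase of another allowed AIHA agent opens the period that runs to Week 24/26 or early termination.
2. **Section 7.1.1 and the matching recording text in Section 7.14.** Record prior use of Table 3 agents for any indication over each agent's own washout length.
3. **Synopsis and Sections 5.9, 6.3, 7.6 and 7.14.1.** Reconcile whether the restriction runs by agent or by indication. Which it should be is a clinical decision and none is proposed here. Item 1 changes only which hemoglobin values count.

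**Cost.** One derivation rule, a longer look-back for a short list of agents, and wording. Concomitant medication is already collected at every visit. The downside is that a few subjects lose eligible visits after treatment given for unrelated reasons.

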#### **7.14.2 Restricted Medications Unrelated to AIHA**

Due to the potential for drug-drug interactions with fostamatinib, the following specific treatments are either not allowed or restricted during the course of the study.

##### **7.14.2.1 Effect of Other Drugs on Fostamatinib**

Drug	Restriction
CYP3A4 inhibitors and inducers	
Concomitant use with strong CYP3A4 inhibitors increases exposure to R406 (the major active metabolite), which may increase the risk of adverse reactions. Monitor for toxicities of fostamatinib that may require dose reduction when given concurrently with a strong CYP3A4 inhibitor.
 
Concomitant use with a strong CYP3A4 inducer reduces exposure to R406. Concomitant use of fostamatinib with strong CYP3A4 inducers is not recommended.

### 7.14.2.2 Effect of Fostamatinib on Other Drugs

CYP3A4 substrates	Concomitant use of fostamatinib may increase concentrations of some CYP3A4 substrate drugs. Monitor for toxicities of CYP3A4 substrate drug that may require dosage reduction when given concurrently with fostamatinib.
BCRP substrates	Concomitant use of fostamatinib may increase concentrations of BCRP substrate drugs (e.g., rosuvastatin). Monitor for toxicities of BCRP substrate drug that may require dosage reduction when given concurrently with fostamatinib.
P-Glycoprotein (P-gp) substrates	Concomitant use of fostamatinib may increase concentrations of P-gp substrates (e.g., digoxin). Monitor for toxicities of the P-gp substrate drug that may require dosage reduction when given concurrently with fostamatinib.

Subjects' concomitant medications should be examined for additional possible drug-drug interactions.

A list of Inhibitors and Inducers of CYP3A4 can be found in [Appendix 4](#).

## **8.0 STUDY DRUG**

### **8.1 Study Drug Description**

Fostamatinib and matching placebo are supplied as orange film coated tablets in 2 dosage strengths: 100 mg and 150 mg. Each bottle of study drug contains 60 tablets. Study drug will be labeled in accordance with Current Good Manufacturing Practices (cGMP)s, local regulatory requirements, and all other applicable laws.

#### **8.1.1 100 mg Tablets**

Fostamatinib 100 mg tablets are supplied as orange film coated, plain, round, biconvex tablets. Each tablet contains 100 mg of fostamatinib and the inactive ingredients of the tablet core are mannitol, sodium bicarbonate, sodium starch glycolate, povidone, magnesium stearate. The inactive ingredients of the film coating are polyvinyl alcohol, titanium dioxide, polyethylene glycol 3350, talc, iron oxide (yellow), and iron oxide (red).

Matching placebo tablets containing magnesium stearate, microcrystalline cellulose and lactose monohydrate. The inactive ingredients of the film coating are polyvinyl alcohol, titanium dioxide, polyethylene glycol 3350, talc, iron oxide (yellow), and iron oxide (red) are supplied.

